**Table 1. Study Termination Rules for Infection and Allergic Reaction:**

Minimum Number of Subjects with Events Meeting Stopping Rule for Infection and Allergic Reaction (infections and/or allergic reactions must be related to the harvesting procedure and/or knee injection) for Selected Numbers of Subjects Randomized Per Treatment Arm at each Center Using a Threshold Incidence Rate of Concern of 10%

Number of Subjects with Event	Number of Randomized Subjects Total	Incidence Rate	Lower 95% Confidence Limit, Wilson score method
1	5	20%	4%
2	5	40%	12%
1	10	10%	2%
2	10	20%	6%
3	10	30%	11%
4	10	40%	17%
4	20	20%	8%
5	20	25%	11%
6	20	30%	15%
5	30	17%	7%
6	30	20%	10%
7	30	23%	12%

Examples above illustrate threshold number of events that exceed the stopping rule (highlighted in bold); non-highlighted entries illustrate the observed incidence rate and the lower 95% confidence limit that does not exceed the stopping rule threshold of 10%

For each treatment arm at each center: if the lower confidence interval for the estimated infection and allergic reaction rate is 10% or higher, then enrollment and randomization will be suspended pending DSMB review. Infection and/or allergic reactions must be related to the harvesting procedure and/or knee injection.

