#### **9.2 Sample Size Determination**

The total estimated sample size for the proposed intention-to treat, parallel-group, multicenter, randomized, controlled trial is 480 subjects. The primary endpoints are Visual Analog Scale (VAS) pain score and the pain subsection of the Knee Injury and Osteoarthritis Outcomes (KOOS). The sample size calculations are based on improvements (from baseline to 1-year) in the visual analog scale (VAS) pain score and total KOOS. Total KOOS was used as a proxy and should ensure that the study is amply powered.

Assuming a decline of 1 point on average in pain in the Control arm (corticosteroids) and a decline on average of 2.5 points in a treatment arm (mesenchymal stem cells) and an estimated standard deviation on change of 3.5, the proposed sample sizes (n=121 subjects

per group or 484 total subjects) will provide 91% power to detect a difference on change of 1.5 points at the two-sided 5% significance level if the true difference between treatment groups is 1.5 points (two-sided two-sample equal variance t-test).

Assuming an increase of 10 points on average in total KOOS in the Control arm (corticosteroids) and an increase on average of 20 points in a treatment arm (mesenchymal stem cells) and an estimated standard deviation on change of 20, the proposed sample sizes (n=121 subjects per group or 484 total subjects) will provide 97% power to detect a difference on change of 10 points at the two-sided 5% significance level if the true difference between treatment groups is 10 points (two-sided two-sample equal variance t-test).

Each of the four participating sites will accrue 30 subjects to each of the 4 treatment groups. Cohort retention is expected to be 90% at 1-year.

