### 9.4.3 Continuous Monitoring of Specific Adverse Events

In addition, the incidence of specific safety related events of concern will be continuously monitored separately in each treatment arm at each center throughout the study to determine if any of their observed subject-based incidence rates exceed a threshold incidence rate of concern pre-specified for each particular event (for example infection and allergic reaction related to study harvest procedure and/or knee injection).

These rules will be implemented by Advanced Clinical continuously monitoring the occurrence of any events to determine if the currently observed rate of each exceeds the corresponding threshold rate of concern with a pre-specified level of confidence. The stopping rule will be considered to be met if the lower 95% confidence limit on the observed incidence rate exceeds the corresponding threshold level of concern for that event. If any stopping rule is met, enrollment and randomization will be suspended pending expedited DSMB review.

The following table describes the minimum number of events out of the selected numbers of subjects randomized to each treatment arm at each site

which, if equaled or exceeded, would satisfy the stopping rule for each event of concern.

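### Table 1 marks 6 events in 30 as meeting the 10% stopping rule, but the Wilson lower limit is 9.5%, so the table and the written rule disagree at that count

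*Combined protocol and SAP*

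**What the plan says.** Section 9.4.3 of the combined protocol and SAP states that specific safety events "will be continuously monitored separately in each treatment arm at each center throughout the study". The rule is met "if the lower 95% confidence limit on the observed incidence rate exceeds the corresponding threshold level of concern for that event". Table 1 is then introduced as listing the smallest event counts that satisfy this rule at selected numbers of subjects.

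The table's title gives the threshold ("Using a Threshold Incidence Rate of Concern of 10" percent), and its last column is headed "Lower 95% Confidence Limit, Wilson score method". The legend says that bold rows exceed the stopping rule and that "non-highlighted entries illustrate the observed incidence rate and the lower 95% confidence limit that does not exceed the stopping rule threshold of 10" percent. The row for 6 events in 30 (20%) is bold, with a printed lower limit of 10%.

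The closing paragraph under the table states the trigger again with a different comparator: enrollment and randomization are suspended pending DSMB review "if the lower confidence interval for the estimated infection and allergic reaction rate is 10% or higher".

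Section 9.2 makes n = 30 the final boundary for each treatment group at each site: "Each of the four participating sites will accrue 30 subjects to each of the 4 treatment groups".

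**The concern.** A limit printed as exactly 10% beside a 10% threshold raises two questions: whether the unrounded value is above or below 10%, and whether equality counts. The plan answers the second question in two ways and does not address the first.

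At 6 events in 30, someone working from the table would suspend enrollment and call for expedited DSMB review; someone working from the formula would not. By n = 30 that group at that site has reached its planned size, so what is at stake is whether the review, and any wider suspension, is triggered. The missing rounding convention also matters between the tabulated sizes, because monitoring is continuous and Table 1 covers only n = 5, 10, 20 and 30.

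**Working it through.** **Inputs.** Threshold 10%, Wilson score method, 95% level, and event counts and sample sizes, all from Section 9.4.3 and Table 1. Planned n of 30 per group per site, from Section 9.2.

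**Formula.** With p = x/n and z = 1.96 (two-sided 95%), the Wilson lower limit is

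L = [p + z²/(2n) − z·√(p(1−p)/n + z²/(4n²))] / (1 + z²/n).

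**Reproducing Table 1.**

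| Events/n | Computed L (%) | Printed (%) | Bold |
|---|---|---|---|
| 1/5 | 3.62 | 4 | no |
| 2/5 | 11.76 | 12 | yes |
| 1/10 | 1.79 | 2 | no |
| 2/10 | 5.67 | 6 | no |
| 3/10 | 10.78 | 11 | yes |
| 4/10 | 16.82 | 17 | yes |
| 4/20 | 8.07 | 8 | no |
| 5/20 | 11.19 | 11 | yes |
| 6/20 | 14.55 | 15 | yes |
| 5/30 | 7.34 | 7 | no |
| **6/30** | **9.505** | **10** | **yes** |
| 7/30 | 11.79 | 12 | yes |

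All 12 printed limits agree at whole-percent rounding, so the method is not in doubt. Of the seven bold rows, only 6/30 has an unrounded limit below 10%.

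**The row in full.** For 6/30: p = 0.2; z²/(2n) = 3.8415/60 = 0.06402; √(0.16/30 + 3.8415/3600) = √(0.005333 + 0.001067) = 0.08000; L = (0.26402 − 1.96 × 0.08000)/(1 + 3.8415/30) = (0.26402 − 0.15680)/1.12805 = 0.09505. For 7/30 the same steps give (0.29736 − 0.16433)/1.12805 = 0.11792.

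**Could another limit be meant?** A one-sided 95% Wilson limit gives 10.71% for 6/30, which would print as 11%. It also gives 14.27% for 2/5 (printed 12%) and 12.69% for 3/10 (printed 11%), so it does not reproduce the table. Continuity-corrected Wilson, Clopper-Pearson, Wald, Jeffreys and Agresti-Coull limits do not reproduce it either.

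**Against the wording.**

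| Reading of 6/30 | Limit must exceed 10% (text before the table; legend) | Limit of 10% or more (paragraph after the table) |
|---|---|---|
| Unrounded, 9.505% | not met | not met |
| As printed, 10% | not met | met |

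Only one of the four combinations supports the bold type.

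**Other sample sizes.** Limits that reach 10% only after whole-percent rounding occur at 2/6 (9.68%), 3/11 (9.75%), 4/17 (9.56%), 5/23 (9.66%), 6/29 (9.85%) and 6/30 (9.505%). Rounding would lower the minimum count by one at each of those n.

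**Size of the effect.** Chance of triggering in one treatment group at one site, by exact recursion over subjects 1 to 30, stopping at the first look where the count reaches the boundary. Assumption: each event is known when the subject is randomized.

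| Looks | True rate | Unrounded rule (7 at n = 30) | Same, but 6 at n = 30 | Rounded at every n |
|---|---|---|---|---|
| Every subject, n = 5 to 30 | 10% | 16.3% | 17.3% | 20.2% |
| Every subject, n = 5 to 30 | 20% | 64.0% | 67.5% | 70.1% |
| n = 5, 10, 20, 30 only | 10% | 13.6% | 15.9% | – |
| n = 5, 10, 20, 30 only | 20% | 56.9% | 65.6% | – |

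The every-subject rows are closest to the continuous monitoring the plan describes. The four-look rows show the effect if only the tabulated sizes were used.

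**The case against.** The strongest reply is that no printed figure is wrong. The value 9.505% rounds correctly to 10%, and on the printed scale the row satisfies the sentence directly beneath the table. On this view there is no miscalculation, only an unstated rounding convention and loose wording. That is a fair description of how the row probably arose. It does not remove the conflict: the reading needs a convention the plan does not give, and the row still fails both the legend and the text before the table, under which a limit of exactly 10% is not enough.

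The second reply is that the window is narrow. The unrounded minimum is already 6 for n = 23 to 28, so six events by subject 28 would have triggered review anyway. If events are known at once, table and formula differ at 6/30 only when the sixth event falls on subject 29 or 30. This stands, and it explains why the shift is only about one percentage point at a true rate of 10%. Late-reported events would widen the window by an amount not quantified here.

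Third, the table errs toward earlier review, the action is suspension pending review, and other safeguards exist. Section 4.5 halts enrollment for any potentially related SAE or at the discretion of the study team, the DSMB, the investigator or the Medical Monitor, and Section 10.8 allows ad hoc DSMB review. This also stands as mitigation, but non-serious infections and allergic reactions do not automatically set off the SAE halt.

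Finally, the four-look and rounded-everywhere figures rest on schemes the plan does not describe. They are sensitivity figures; the conclusion rests on the n = 30 change under looks at every subject.

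**Conclusion.** The concern holds. At the planned n of 30 per group per site, Table 1 gives 6 as a count that meets the stopping rule, while the rule computed by the plan's own method is first met at 7. The two statements of the rule also differ on whether equality counts.

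The practical effect is small and cautious in direction: about 0.9 percentage points (16.34% to 17.26%) in the chance of a trigger in one group at one site at a true rate of 10%, and 3.5 points (64.01% to 67.50%) at 20%. These figures assume looks after every subject from n = 5 and immediate knowledge of events; the starting look is a choice made for this check. The disagreement at 6/30 itself needs no such assumption. A pre-specified safety trigger should give one answer for a given count, and this one does not.

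**What to change.** In Section 9.4.3, use one comparator in the text before Table 1, the legend and the paragraph after it. State whether the comparison uses the unrounded limit or, if not, the rounding convention. Print the limits to one decimal, and reconcile the 6/30 row with the rule so stated. The sponsor and the DSMB should confirm which boundary at n = 30 is intended; this review does not choose between them.

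A table of minimum counts for every n from 1 to 30 would help whoever runs the continuous monitoring, but is optional.

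The cost is one table row and one sentence, with the limits reprinted. The DSMB charter was not available for this review, and any matching text in it should be checked.

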#### 9.4.4 Analysis of Adverse Events

Additionally, the following AE-related specific analysis will be performed.

1. Frequency and percentages of each event will be summarized by treatment arm for the following:

- AEs
  - AE in relationship to study treatment (not-related, possibly related, or related)
  - AE Severity
  - SAEs
  - SAE in relationship to study treatment (not-related, possibly related or related)
  - SAE Severity
  - Any Laboratory Toxicities
2. Allergic reaction and infection will be summarized as one category and corresponding number and proportions will be provided for each CTCAE grade level by treatment arm. These AEs will be counted only once per subject as the most severe level (i.e., maximum severity) reported across the six study assessments/visits during the 1-year follow-up period and compared between treatment arms with a chi-square or Fisher's exact test. The 95% confidence intervals will also be provided for the proportions.
  3. Estimates of infection at harvest site or treated/targeted knee by treatment arms and time on study will be estimated and compared by performing a generalized estimating equations (GEE) analysis of the repeated binary responses within participant. The subjects will be clustered within center. This analysis will be implemented via the SAS GENMOD Procedure, using an exchangeable correlation structure for the repeated data within subjects (binomial-logit model). Infection rates and 95% confidence intervals will be used to summarize the data by treatment group and clinical visit.
  4. Subjects who become pregnant while on the study will be followed for AEs/SAEs that may occur for up to 30 days following the birth of the child.

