### **6.2.2 Implementation of Randomization and Blinding**

Subjects randomized to Arm 1 or Arm 2 will undergo a procedure (bone marrow aspiration or liposuction) but will only receive one of the possible injections. For instance, subjects randomized to the control portion of Arm 1 will undergo a bone marrow aspiration but will receive a blinded corticosteroid injection. The bone marrow aspirate will still be processed and used to help quantify cell characteristics. Subjects randomized to Arm 3 will not undergo the procedures mentioned above. They will be blinded and receive either the stem cell injection or the corticosteroid injection.

Four hundred eighty subjects will be randomly assigned to treatment in this multicenter trial. Subjects at each clinical site will be randomized to ensure the trial is single-blind with a 1:1 allocation ratio across the four treatment groups.

One hundred twenty subjects will be randomized at each of 4 clinical sites. Arm 1: Forty subjects will be randomized with a 3:1 allocation ratio (bone marrow derived MSCs versus corticosteroid injection; 30:10). This same implementation plan will be used to randomize 40 subjects to Arm 2 (adipose derived MSCs versus corticosteroid injection) with a 3:1 allocation ratio and to randomize 40 subjects to Arm 3 (umbilical cord tissue MSCs versus corticosteroid injection) with a 3:1 allocation ratio.

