#### **8.4.3 AE and SAE Collection**

All AEs and SAEs will be collected from the signing of the informed consent form until the one-year follow-up visit at the time points specified in the SoA (Section 1.3) as required by applicable regulation and best practice.

All SAEs will be recorded and reported to the sponsor and the pharmacovigilance team at Advanced Clinical within 24 hours of the study personnel becoming aware of the event. Please utilize the approved SAE data collection forms provided by Advanced Clinical to submit the notifications and updates. The investigator will submit any updated SAE data to the sponsor within 24 hours of it being available.

Investigators are not obligated to actively seek AE or SAE after conclusion of the study participation. However, if the investigator learns of any SAE, including a death, at any time after a subject has been discharged from the study up to a 30 day follow-up period, and he/she considers the event to be reasonably related to the study intervention or study participation, the investigator must promptly notify the sponsor.

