### **9.3.3 Efficacy Analyses across Subgroups**

The heterogeneity of treatment effects across age, sex, and ethnicity will be evaluated using a statistical test for interaction terms. Specifically, effects of treatment in subgroups will be determined by including the additional interaction terms between treatment and the three subgroups (age, sex, and ethnicity) in the repeated measures model described above for the eight efficacy variables.

The following variables will be treated as categorical variables in all of the linear mixed models.

- Treatment arms: CSI (reference), BMAC, ADP, UCT
- Age:  $\leq 65$  (reference) vs.  $>65$
- Sex: female vs male (reference)

- Ethnicity: Hispanic vs non-Hispanic
- Time: 0, 1, 2, 3, 4, 5 representing baseline and 1, 3, 6, 9 and 12 months follow-up visits

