### 9.4.2 Adverse Events

All adverse events (AEs) and serious adverse events (SAEs) will be classified by System Organ Class (SOC) and Preferred Term (PT) according to the Medical Dictionary of Regulatory Activities (MedDRA) version 21.1 for the safety population. The number and percentage of subjects reporting AEs, as well as the number of events, in each treatment group will be tabulated by SOC and PT; by SOC, PT, and maximum severity; and in relationship to study treatment, SOC and PT. If a subject has multiple occurrences of the same SOC and PT, then the subject will be counted only once for the SOC and PT using the most severe occurrence for the summarization by maximum severity. Presentation by SOC and PT will display SOC sorted alphabetically and PT by descending frequency within SOC.

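### Pooled steroid controls are two-thirds harvested and UCT subjects are not, so the adverse event tables will tend to show more events on CSI than on UCT even if the injections are equally safe

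*Combined protocol and SAP*

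**What the plan says.** - **Attribution.** The first item of Section 9.4.4 summarises adverse events by treatment arm using "AE in relationship to study treatment (not-related, possibly related, or related" as its three levels. Section 9.4.2 tabulates them "in relationship to study treatment, SOC and PT". Neither section divides study treatment into harvest and injection.
- **Groups.** Section 9.4.2 states: "The number and percentage of subjects reporting AEs, as well as the number of events, in each treatment group will be tabulated". The only coded list of groups, in Section 9.3.3, reads "Treatment arms: CSI (reference), BMAC, ADP, UCT". Section 9.4.1 likewise plans four treatment listings (BMAC, UCT, SVF and CSI).
- **Who is harvested.** Section 6.2.2 says that "subjects randomized to the control portion of Arm 1 will undergo a bone marrow aspiration but will receive a blinded corticosteroid injection", and it applies the same approach to liposuction in Arm 2. It then says "Subjects randomized to Arm 3 will not undergo the procedures mentioned above".
- **Comparisons.** Section 9.4.4 combines infection and allergic reaction into one category, tested between arms by chi-square or Fisher's exact test. It also fits a GEE to infection at either the harvest site or the knee, as a single endpoint.

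**The concern.** Every subject has a knee injection, but only Arms 1 and 2 have a harvest as well, and their steroid controls have it too. Section 2.3.1 lists the harvest risks apart from the injection risks. A liposuction haematoma in an Arm 2 steroid control enters the CSI column, where nothing in the planned tables separates it from an effect of the injection. The UCT column cannot contain such an event. A reader of the four-column table would take the CSI-UCT difference as a difference between injected products, although part of it comes from the sham harvest. The BMAC and SVF columns are set against a control in which two-thirds of subjects were harvested. That contrast measures neither the injection alone nor the whole strategy against a plain steroid injection. Section 4.1 names safety alongside efficacy as something the trial tests, so these tables matter.

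**Working it through.** The plan gives no figure for this comparison. Its nearest safety figures, the twelve Wilson lower limits in Table 1, reproduce after rounding and are not in dispute.

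**Harvest exposure (Synopsis, Section 6.2.2).** Each arm has 120 product and 40 steroid subjects. Harvested: BMAC 120/120, SVF 120/120, CSI (40 + 40)/120 = 66.7%, UCT 0/120.

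**Model.** Let r be the injection event rate, equal in CSI and UCT, and h the harvest event rate, equal for both harvests and independent of r.

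- Unharvested subject: r
- Harvested subject: 1 - (1 - r)(1 - h)
- Pooled CSI minus UCT: (2/3)h(1 - r)
- BMAC or SVF minus pooled CSI: (1/3)h(1 - r)

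**Example, r = h = 10%.** Harvested: 1 - 0.9 × 0.9 = 19.0%. Pooled CSI: (80 × 0.19 + 40 × 0.10)/120 = 19.2/120 = 16.0%. UCT: 10.0%. The gap is 6.0 points with equally safe injections. BMAC exceeds pooled CSI by 3.0 points. It would exceed an unharvested control by 9.0 points and an equally harvested control by 0.

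**Range for any event.** The rates are assumptions. Section 2.3.1 gives bands per listed event: 10-20% for the more frequent harvest effects, and up to 20% for mild local pain or swelling after the knee injection. The last column is the exact probability that a Pearson chi-square of CSI against UCT (120 v 120) reaches two-sided p<0.05, with CSI counts formed as Bin(80) + Bin(40).

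| r | h | UCT | Pooled CSI | Gap (points) | P(p<0.05) |
|---|---|---|---|---|---|
| 5% | 10% | 5.0% | 11.3% | 6.3 | 45.2% |
| 5% | 20% | 5.0% | 17.7% | 12.7 | 90.1% |
| 10% | 10% | 10.0% | 16.0% | 6.0 | 28.1% |
| 10% | 20% | 10.0% | 22.0% | 12.0 | 73.5% |
| 20% | 10% | 20.0% | 25.3% | 5.3 | 16.7% |
| 20% | 20% | 20.0% | 30.7% | 10.7 | 47.9% |

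No test of any-event rates is planned, so for these rows the last column only shows how visible the gap would be.

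**Infection and allergic reaction, which are tested.** Section 2.3.1 puts infection after either harvest in the 1-10% band. With r and h each taken as 5% or 10%, the probabilities are:

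- r = 5%, h = 5%: 17.1%
- r = 5%, h = 10%: 45.2%
- r = 10%, h = 5%: 11.2%
- r = 10%, h = 10%: 28.1%

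The range is therefore about 11-45%. At the bottom of the band the effect is small: h = 1% and r = 10% give (2/3)(0.01)(0.9) = 0.6 points.

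**Within-arm contrast.** UCT against Arm 3 CSI has no harvest on either side, so the spurious gap is 0. The chi-square for 120 v 40 has type I error of 4.0-5.0% for r = 5-20%. At r = 10% the 95% half-width is 1.96√(0.09(1/120 + 1/40)) = 10.7 points, against 1.96√(0.09 × 2/120) = 7.6 points for 120 v 120.

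**The case against.** The case against has five parts.

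- **Harvest is not ignored.** Table 1 requires that "infections and/or allergic reactions must be related to the harvesting procedure and/or knee injection", and the GEE names the harvest site. A reader might infer that harvest is overlooked throughout, and that is not so. But both places join the two sources, so neither removes the imbalance. For the stopping rule this is no defect: it counts events from either source and needs no separation. Coding by system organ class and preferred term may reveal some harvest events, but infection or haematoma need not identify its site.
- **Counting from consent.** Section 8.4.3 says "All AEs and SAEs will be collected from the signing of the informed consent form until the one-year follow-up visit", and a reader might infer that events before the procedure also favour UCT. They do not. Randomization precedes the treatment visit, so they fall alike on all groups. If they occur at rate q, the gap is multiplied by (1 - q): with r = 10% and h = 15% it goes from 9.0 points at q = 0 to 8.1 at q = 10%. The infection/allergy comparison is in any case confined to follow-up visits. The absent treatment-emergent definition is a missing detail, not a source of this bias.
- **Harvest events alone.** Applying 10-20% to 80 harvested controls gives 8 to 16 CSI events against none on UCT, and a very small p-value. No such table is planned. It would leave out the injection background, and the 10-20% bands do not contain infection, which is what is tested.
- **Harvest belongs to BMAC and SVF.** This stands. Counting its harms there is legitimate; the distortion lies in the pooled CSI comparator.
- **The answer may lie elsewhere.** Section 9.3 refers to a SAP describing the analysis populations. No separate SAP text was available, nor an adverse event form, so a rule there cannot be excluded. The protocol's own safety section contains none.

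**Conclusion.** The concern holds as a bias in the pooled CSI safety comparator. As written, the tables, the infection/allergy test and the infection GEE all set a control group that is 66.7% harvested against a UCT group that is 0% harvested. With equally safe injections the expected excess on CSI is (2/3)h(1 - r): 5.3 to 12.7 points for r = 5-20% and h = 10-20%. For the tested category, the chance of a false p<0.05 is about 11-45% when r and h are each 5-10%.

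Three assumptions carry this result. CSI is pooled across arms, which Sections 9.3.3 and 9.4.1 indicate but Section 9.4.4 does not state. The rates are chosen from per-event bands; the rate of any harvest event could exceed 20%, and the infection rate could be well below 5%. The test is read as CSI against UCT at two-sided 0.05, a detail the section leaves open.

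It would go too far to say that UCT will look safer. This is a tendency that depends on h, and Section 2.3.1 lists an allergic-reaction risk of UCT's own that could offset it.

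**What to change.** 1. Report CSI adverse events by arm. Make the safety comparisons within arm: BMAC v Arm 1 CSI, SVF v Arm 2 CSI, UCT v Arm 3 CSI. Both sides then have the same harvest exposure and are randomized within the arm, and no causality judgement is needed.
2. Record relatedness to the harvest and to the knee injection separately. Tabulate injection-related events by product and harvest-related events by harvest type, so that the burden of the whole BMAC or SVF strategy stays visible.
3. Analyse harvest-site infection and knee infection as separate endpoints, with the former confined to Arms 1 and 2.

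The main cost is precision, because each contrast becomes 120 v 40, with the wider interval shown above. The rest is table programming, possibly one field on the adverse event form, and re-attribution from source of events already recorded. The attribution in step 2 rests on investigator judgement in a single-blind trial, so it should support step 1 and not replace it. The design, sample size and efficacy analysis are unaffected.
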